1.1 Substantial protocol amendment

This global substantial amendment has been prepared to:

- enable performing Visit 1 and Visit 2 at the same day
- revise inclusion criterion no.2 and exclusion criterion no. 4
- delete inclusion criterion no.5 and exclusion criterion no. 6
- extend the number of required exposure days (ED) from 50 to 100
- analyse haematology samples at the central lab.

In this substantial protocol amendment:

- any new text is written in *italics*
- any text deleted from the protocol is written using ~~strike through~~.

Minor changes that do not affect the content of the protocol will not be disclosed in the following sections e.g.:

- the substance code NNC 0155-0000-0004 will be exchanged for turoctocog alfa
- minor inconsistencies and ambiguities
- typographical errors.

1.2 Rationale for amendment No. 6

The main focus of this amendment is enabling performing Visits 1 and 2 at the same day. The current clinical trial includes Previously Untreated Patients (PUP), and the protocol demands blood sampling at the first visit in the trial. This constitutes a risk for bleeds. For the safety of these untreated patients, we will make it possible to administer trial product already at the first visit to the clinic. This can be accomplished if Visit 1 and Visit 2 are performed at the same time, without waiting for lab result from screening assessments.

Changes to the eligibility criteria, i.e. deletion of inclusion criterion #5 and exclusion criteria and #6, and revising inclusion criterion #2 and exclusion criterion #4, are following considerations of relevance. Immune competency will be present in the vast majority of PUPs and inclusion criterion #5 can thus be regarded as unnecessary. Presence of FVIII inhibitors, $0.6 \geq BU$, (exclusion criterion #4) can be considered as highly improbable in a true PUP population. Similarly, thrombocytopenia with platelets $\leq 50000/\mu l$ (exclusion criterion #6) will also very rarely, if ever, be seen in these haemophilic patients. The above mentioned parameters will be captured as baseline characteristics,

but not for eligibility.

It is our strong opinion that changing the above criteria will in not compromise the safety of the patients enrolled in the trial. Patients with any disease or condition which might pose a potential hazard are not eligible according to the unchanged exclusion criterion #7.

2 Changes

2.1 1 Summary

Trial Design

The trial consists of two phases. In the main phase, an aggregated number of at least 50 patients will receive preventive treatment with *turoctocog alfa NNC 0155-0000-0004* until they reach a minimum of 50 exposure days (ED) or until they develop inhibitors. After that the patient will continue in the extension phase *until at least 100 ED has been achieved*, which will *translate into a maximum of last for approximately 3.5 years*. The estimated total duration of the trial is approximately 5 years.

Trial Population

Approximately 60 PUP with severe (~~baseline level~~ FVIII $\leq 1\%$) haemophilia A without *no history of* inhibitors below 6 years of age in a non-bleeding state will be enroled to allow for at least 50 patients to complete the trial.

Key Inclusion Criteria:

- ---
- Male patients *diagnosed* with congenital severe haemophilia A (~~baseline level~~ FVIII $\leq 1\%$)

Key exclusion Criteria:

- ---
- *Any history of* FVIII inhibitor ($\geq 0.6 \text{ BU/mL}$) *at screening*
- ---
- ~~Platelet count <50,000 platelets/ μL~~

2.2 2 Flow Chart

(Clarification note: For Table 2-1 and 2-2 only information that is subjected to changes is presented.)

Table 2-1 Visit Flow Chart main trial phase

[figure not shown]
Visit number	Screen. Visit 1	Visit 2 [#]	Visit 3	Visit 4	Visit 5	Unscheduled Visit
Visit window	NA	<214±7 d post V1	10 th -15 th ED	20 th -25 th ED	50±00 th - 55±10 th ED	

Visit 2 can be performed at the same day as Visit 1

Table 2-2 Visit Flow Chart trial extension phase

Visit type	Dispensing		Assessment& Dispensing	Dispensing		Assessment& Dispensing	End of Trial	Unsch Visit
Visit number [#]	6	7	8	9	10	11		
Previous visit time(w)	-8	-8	-10	-8	-8	-10	< 8	
Visit window	± 1w	± 1w	± 1w	± 1w	± 1w	± 1w	NA	NA
ASSESSMENTS								
SAFETY								
FVIII trough level	•a	•a	•a	•a	•a	•a		•a

a – optional, at discretion of investigator

Screening will be done at Visit 1, ~~14 ± 7 days prior to Visit 2 will be performed within 21 days post Visit 1, and it could be the same day as Visit 1~~. At Visit 2 eligible patients are enrolled and preventive treatment with investigational product (turoctocog alfa) starts if applicable (may start after the first two bleeds). At Visit 5, after ≥ 50 ED, patients will leave the main phase of the trial and continue in the extension phase. Patients who develop inhibitors can continue with ITI treatment with an alternative visit schedule (down ward arrows). If ITI treatment is successful these patients can continue with preventive treatment according to the extension phase (upward arrows). The patients will belong to either of the groups main-phase, extension phase or inhibitor cohort.

Figure 2–1 Trial Design

2.3 3.1.1.2 Risks and Benefits

After the patients have achieved the required number of ED, they may ~~will~~ *continue in the trial until product launch or until the end of trial, should market authorisation not be obtained, see Section 7. This serves to minimise the patients' need of switching to other FVIII products*

2.4 5.1 Type of Trial

The trial consists of two phases i.e. main and extension, respectively. In the main phase the patients will attend a screening visit (Visit 1) in order to assess their eligibility. At Visit 2 eligible patients will receive their first dose, if applicable. *It is an option to perform Visit 1 and Visit 2 at the same day for the purpose of immediate administration of the trial product. After Visit 2 the patients* ~~and~~ *will be scheduled for 3 more visits in the main phase. After Visit 5 the patients will enter the extension phase, and a rolling visit schedule will apply with 6 planned visits (including 4 dispensing visits) per year.*

The main trial phase will be completed when the aggregated number of patients, who have either received treatment with turoctocog alfa for at least 50 ED or developed inhibitors, are at least 50. *In the extension phase the patients will be followed until at least 100 ED has been achieved.* For the individual patient it translates into duration of the main phase of approximately 3-24 months depending on the dose regimens (and bleeding pattern). The duration of the extension phase may be up to 3.5 years, and the total duration of the trial is estimated to be approximately 5 years, please see Section 7.

2.5 5.3 Treatment of Patients

Approximately 60 patients are expected to be enrolled (*trial drug administered*) into the trial in order to have 50 evaluable patients, *who complete in the main phase of the trial* (estimated drop-out rate is 15%). For replacement of withdrawn patients, please refer to Section 6.5.

2.6 6.2 Inclusion Criteria

2. Male patients *diagnosed* with congenital severe haemophilia A (FVIII level $\leq 1\%$)*

5. ~~Immunocompetent, defined as either HIV negative or if HIV positive, CD4⁺ cells > 200 cells/ μ L~~

*based on the one stage clotting assay

2.7 6.3 Exclusion Criteria

4. *Any history of* FVIII inhibitor (≥ 0.6 BU/mL) *at screening*

6. Platelet count $< 50,000$ platelets/ μ L

2.8 6.5 Patient Replacement

Withdrawn patients may be replaced to ensure that 50 patients complete the trial with at least 50 100 ED. Assuming a drop-out rate of 15%, it is estimated that 60 patients must be enroled to obtain the 50 completed patients. This may, however, be adjusted during the trial based on the actual drop-out rate.

2.9 6.6 Rationale for Trial Population

Rational for Exclusion Criteria:

- Criteria on nos. 3 and 6 are chosen to exclude patients with endogenous abnormalities of the coagulation system other than haemophilia

2.10 7

Trial Schedule

Planned completion of clinical trial report (CTR): ~~Q3 2016~~ *Q1 2017*

2.11 8.1.3

Visit 2

The visit will be scheduled *within 21–14±7* days after *Visit 1*.

The main purpose of Visit 2 is to administer turoctocog alfa for the first time, if applicable, or *alternatively dispense the trial product* to eligible patients.

2.12 8.1.3.1

Combining Visit 1 and Visit 2

Visit 1 and Visit 2 can be performed at the same day. It will allow for immediate administration of trial product should this be preferred or deemed necessary.

Please ensure that all assessments required for Visit 1 and Visit 2 are performed and that all required blood samples for the central laboratory is taken before the administration of the trial product.

2.13 8.2.2

FVIII Inhibitors

All patients will be examined regularly for the development of FVIII neutralising antibodies (inhibitors). The tests will be performed at Visit 1 (*baseline characteristics*) and Visits 3–5 in the main phase of the trial, and at the Assessment&Dispensing and EoT Visits in the extension phase, i.e. at least twice annually. Additional laboratory assessment for FVIII neutralising antibodies can be done if inhibitor development is suspected during the course of the trial, or if more frequent testing is mandated i.e. during unscheduled visits.

2.14 8.2.3

FVIII Recovery Assessments

2.15 8.2.3.1

FVIII Activity

In order to establish patient characteristics, baseline FVIII activity will be taken at Visit 1. Any anti-haemophilic treatment with blood components should be withdrawn at least 48 hours prior to blood sampling.

2.16 8.2.3 8.2.3.2

FVIII Recovery

Recovery is the FVIII plasma level recorded 30 ± 5 minutes after trial product administration and reported as [IU/mL]/[IU/kg]. Recovery assessment is mandatory at inhibitor diagnosis to identify

clinical relevant inhibitors (see Section 8.2.2). Additional recovery assessments may be requested at the discretion of the Investigator.

Samples for FVIII recovery will be sent to the central laboratory for analysis, see Section [8.2.7.2](#).

2.17 8.2.4 8.2.3.3 FVIII Trough Level Assessment

The Investigator can at his/her discretion perform trough level assessments at *any visit during the trial, except Visit 3-4 1-2*. The trough level is defined as the lowest level of FVIII measured immediately prior to dosing and reported as (IU/mL). The trough level will be determined at the local laboratory.

Trough levels need only to be recorded in the eCRF if it is the reason for dose adjustments.

2.18 8.2.5 Haematology

The assessment will be performed at Visit 1 and Visit 5 in the main phase, the Assessment&Dispensing Visits in the extension phase, EoT Visit and optionally at unscheduled visits. It is performed according to practice of the *central local* laboratory and includes:

~~It is recommended that the haematology values are reported in the above listed units. However, in the eCRF it will be possible to enter values in other units accepted by Novo Nordisk.~~

2.19 8.2.7.2 Local Laboratory Tests

Assessments of ~~haematology~~, FVIII trough levels and ~~CD4⁺ T cell count (if applicable)~~ will be done at the local laboratory* as per standard of practice at the participating site. Laboratory results from the local laboratory will be recorded in the eCRF.

~~*in Russia and Hong Kong, CD4+~~

~~T cell count is done centrally~~

2.20 8.2.7.3 Central Laboratory Tests

A central laboratory will coordinate analysis and report of all laboratory safety tests related to biochemistry, viral antibody assessments ~~except CD4⁺ T cell count~~, FVIII inhibitor, FVIII activity and genotyping performed in this trial. Laboratory data from the central laboratory will be reported to Novo Nordisk electronically, and in a manner that anonymity of patients will be maintained.

2.21 8.4.5 Diaries

Diaries will be dispensed and reviewed at all visits, ~~except visits 1, 2 and EoT starting from Visit 2.~~

2.22 12.1.2 Medical Event of Special Interest and other events for expedited reporting

- Inhibitor formation against FVIII
 - *Inhibitor formation is always considered a MESI.* Blood samples for measurements of FVIII inhibitors will be analysed at the central laboratory selected by Novo Nordisk. *However, if an investigator obtains any indication of inhibitor formation by clinical signs or local laboratory results, it should be reported as MESIs.* *The diagnosis of inhibitor is made, if the patient has been tested positive for inhibitors (BU \geq 0.6/mL) at two consecutive tests at the central laboratory, sampled preferably within 2 weeks.* ~~this should be reported by the Investigator as a MESI~~ *However, if the first inhibitor test is positive, it should also be reported as a MESI even though the confirmatory test is negative.*

2.23 23 Responsibilities

The following will be analysed at the local laboratory: ~~haematology~~, FVIII trough level assessment and ~~CD4+ T cell (excluding Russia)~~.

Central and specialized laboratories will analyse and report all laboratory safety tests related to biochemistry, *haematology*, viral antibody assessments, FVIII activity, FVIII inhibitor assessments and potential genotyping performed in this trial. Laboratory data from the central laboratory will be reported to Novo Nordisk electronically. Laboratory data will be reported to Novo Nordisk in a manner that anonymity of patients will be maintained.

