- Incidence rate of inhibitors defined as inhibitor titres ≥ 0.6 Bethesda units/mL *for the main phase of the trial*

The incidence rate of inhibitors will be calculated and a 1-sided 97.5% upper confidence limit will be provided based on an exact calculation for a binomial distribution. For the calculation of the incidence rate the numerator will include *number of all patients with inhibitors* while the denominator will include *number of all patients with confirmed inhibitors during the main phase of trial or completed the main phase without confirmed minimum of 50 ED plus any patients with less than 50 ED but with inhibitors*.

2.44 18.2.4 Supportive Secondary Endpoints

All the below efficacy endpoints will be evaluated for the main phase of trial, for the extension phase of trial, and for the combined main and extension phases. Sensitivity analyses will be made only including patients who do not develop inhibitors during the main phase of the trial and during the extension phase of the trial. For patients that develop inhibitors only the time period until the last negative inhibitor result is considered for the efficacy endpoints below. Sensitivity analyses will be made only including patients who do not develop inhibitors. Further, tables will be made including only inhibitor patients. For these patients the relevant time period is the time period after positive inhibitor test.

Secondary Efficacy Endpoints

- Annualized bleeding rate during bleeding prevention period with turoctocog alfa

For this endpoint patients who develop inhibitors will only be included if they have been treated *with at least two doses of trial product for minimum 1 month* before the first positive inhibitor test. The reason to exclude these patients from the calculations is *that if the treatment period is too short, that the information from the treatment with one dose is too small and the uncertainty introduced on the estimated annualized bleeding rate will be relatively large.*

Separate reports and listings will be made for the above efficacy endpoints for patients developing inhibitors. Data used in these reports and listings will include data from the first time patient is confirmed with inhibitors until the end of the main phase of trial as well as until the end of trial. Furthermore, each of these reports will also be generated for different method for management of patients with inhibitors.

Secondary Safety Endpoints

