- No prior use of purified clotting factor products (previous exposure, *equal to or less than 5 ED to blood components, e.g. cryoprecipitate, fresh frozen plasma* is accepted)

2.2 2 Flow Chart

(Clarification note: For Table 2-1 and 2-2 only information that is subjected to changes is presented.)

Table 2-1 Visit Flow Chart main trial phase

Visit number [#]	Screen. Visit 1	Visit 2 [#]	Visit 3	Visit 4	Visit 5	Unscheduled Visit
Visit window	NA	≤ 21 d post V1	10 th -15 th ED	20 th -25 th ED	50 th -55 th ED	
SAFETY						
Consent for FVIII genotype test	●					
Antibodies						
- FVIII inhibitors	●a		●a	●a	●a	●a, b
- FVIII non-neutralising antibodies						
Trial Material						
Diary and Trial card dispensing and/or collection^e	●e	●e	●e	●e	●e	●b
Drug dispensing and accountability		●g	●	●	●	●b
Diary card training		●				

- Visit 2 can be performed at the same day as Visit 1

a – minimum 48 hours washout period of turoctocog alfa (or blood component products at Visit 1)

b – if applicable

e - Visit 1 trial card only, Visit 2-4-5 diary card only

g - Visit 2 dispensing only, Visit 5 accountability only

Table 2-2 Visit Flow Chart trial extension phase

Visit type	Dispensing		Assessment& Dispensing		Dispensing		Assessment& Dispensing	End of Trial	Unsch Visit
Visit number[#]	6	7	8		9	10	11		
Previous visit time(w)	-8	-8	-10		-8	-8	-10	< 8	
Visit window	± 1w	± 1w	± 1w		± 1w	± 1w	± 1w	NA	NA
SAFETY									
Antibodies									
- FVIII inhibitors	●a	●a	●		●a	●a	●	●	●a
- FVIII non-neutralising antibodies									

- Presented numbers are for the first 12 months. Visit numbers for future years will be in consecutive order

a – optional, at discretion of investigator

Caption text (Figure 2–1 Trial Design)

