9.5 Trial Product Administration

The IV/WRS will report the dosing volume of turoctocog alfa to be injected based on the patient's weight and dose IU/kg.

The trial product should be administered as a slow bolus i.v. injection over approximately 2 min. (from start to completion of injection) for all trial product administrations.

~~These administrations will primarily be performed at home. All patients and/or parents/caregivers will be instructed by Investigator how to handle home administration before first dose.~~

...

11 Concomitant Illnesses and Concomitant Medication

...

The following concomitant medications are not permitted during the course of this trial:

- Treatment with FVIII concentrates other than the trial product, see Section 6.4.

Treatment with blood and blood component products containing FVIII, e.g. cryoprecipitate and plasma, except during surgery, should be avoided.

~~In case these medications are used during the trial, the patient must be withdrawn. The use of these medications during the course of the trial may lead to patient withdrawal as described in Section 6.4.~~

...

12 Adverse Events

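### Since Amendment 6, a confirmed inhibitor already present in the pre-dose Visit 1 sample would count as a case in the primary rate and in the enrolment-hold tally

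*Combined protocol and SAP*

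**What the plan says.** **Eligibility.** The 2011 protocol (6.3, criterion 4) excluded an inhibitor of 0.6 BU/mL or more at screening. Amendment 6 changes this to a history of inhibitor. Its rationale (1.2) says of the dropped or revised laboratory criteria: "The above mentioned parameters will be captured as baseline characteristics", "but not for eligibility". It judges an inhibitor in a true previously untreated patient to be highly improbable.

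**Dosing before the result.** The same rationale allows treatment at the first clinic visit "without waiting for lab result from screening assessments". Of combined visits, new section 8.1.3.1 says "It will allow for immediate administration of trial product should this be preferred or deemed necessary". Central-laboratory blood must be drawn before that dose.

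**Testing and diagnosis.** Section 8.2.2 (Amendment 6) schedules inhibitor tests at Visit 1, labelled as baseline characteristics, and at Visits 3 to 5. Section 8.2.2.1 makes the diagnosis on two consecutive central results of at least 0.6 BU/mL. It does not ask for a negative baseline.

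**Counting.** Section 18.2.2, as revised when the main and extension phases were introduced, reads "For the calculation of the incidence rate the numerator will include" and goes on to name all patients with inhibitors. The denominator is patients with a confirmed inhibitor in the main phase plus those who completed it without one. The hold rule (12.5.2 and 18.3) uses the same two-test diagnosis and triggers at 12 cases.

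**Prior exposure.** Amendment 7 accepts previous exposure "equal to or less than 5 ED to blood components". Section 11, in the last amendment, refers to "Treatment with blood and blood component products containing FVIII, e.g. cryoprecipitate and plasma".

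**The concern.** The primary endpoint and the hold rule exist to measure inhibitors that arise on turoctocog alfa. Section 6.6 of the 2011 protocol gave that purpose for criterion 4: to keep out boys who had an inhibitor before treatment started. Amendment 6 removed the laboratory check and put nothing in the analysis in its place.

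The sponsor recognises the general risk elsewhere. The later amendment that bars prior use of the commercial product does so because inhibitors that arise before enrolment could bias the primary endpoint.

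At stake is the attribution of individual cases. In a trial of about 50 evaluable boys, one misattributed case is visible in the primary estimate and uses up one of the 12 that stop enrolment. If the question is settled only after such a boy appears, the decision on a primary case is made post hoc.

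**Working it through.** **Sample size, for orientation.** Section 6.5 (Amendment 6) wants 50 completed patients at 15% drop-out: 50/(1 − 0.15) = 58.8, so 59, which agrees with the stated figure of about 60. The point does not depend on this figure.

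**Path through the rules for one boy**
1. He has no known inhibitor history, so revised criterion 4 does not exclude him.
2. Visits 1 and 2 are on the same day. The sample is drawn, then he is dosed without a result.
3. Visit 1 returns at or above 0.6 BU/mL and a confirmatory sample is taken. If it is also positive, he meets the diagnosis in 8.2.2.1.
4. He enters the numerator and denominator of 18.2.2 and the hold count.

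**Would the endpoint window stop this?** Amendment 1 started the window at Visit 2. The latest summary wording says only that the endpoint is evaluated for the main phase, and section 5.1 places Visit 1 in that phase. Even with a start at Visit 2, a persistent positive would be found at the confirmatory test and at Visit 3. The window is therefore not a reliable safeguard.

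**Primary rate.** The upper limit is the one-sided 97.5% exact binomial limit of 18.2.2, which is the 0.975 quantile of Beta(x + 1, n − x). Assume 50 evaluable boys, of whom k have a confirmed pre-dose positive. The number of truly incident cases is assumed: 15 (30% of 50) or 17 (34%), within or at the edge of the plan's expected 30–35%. The fair contrast removes the k boys from both numerator and denominator.

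| Incident | k | As written | Upper limit | k removed | Upper limit |
|---|---|---|---|---|---|
| 15 | 1 | 16/50 = 32.0% | 46.7% | 15/49 = 30.6% | 45.4% |
| 15 | 2 | 17/50 = 34.0% | 48.8% | 15/48 = 31.3% | 46.3% |
| 17 | 1 | 18/50 = 36.0% | 50.8% | 17/49 = 34.7% | 49.6% |

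One such boy moves the estimate by 1.3 to 1.4 points and the upper limit by 1.2 to 1.3 points.

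**Hold rule.** Take 25 exposed boys at the interim, independent and with a common rate. This is a simplification, because the rule counts all boys exposed by then.

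| Situation | Probability | 30% rate | 35% rate |
|---|---|---|---|
| No pre-dose positive | P(at least 12 of 25) | 4.4% | 12.5% |
| One pre-dose positive, counted | P(at least 11 of the other 24) | 7.4% | 18.3% |
| One pre-dose positive, removed and not replaced | P(at least 12 of 24) | 3.1% | 9.4% |

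**How likely is such a boy?** The documents give no prevalence. If it were 0.1%, 0.5% or 1% (assumed), the chance of at least one among 60 is 1 − (1 − p)^60 = 5.8%, 26.0% or 45.3%.

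**The case against.** The strongest reply is that incidence, development and inhibitor formation all mean new onset, that the Visit 1 test is labelled as baseline, and that no sensible analyst would count a pre-dose positive. That is the natural intent, but no counting rule in the available text states it, and the two-test definition read literally includes him.

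Other parts of the reply stand and limit the point:

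- A reader might infer that a baseline-positive boy always stays in. The documents do not go that far. The current flow chart checks eligibility at both Visit 1 and Visit 2. If the visits are separated and the result is back, the investigator might treat it as history, or use criterion 7, although the Amendment 6 rationale points the other way. The clear gap is same-day dosing or a late result.
- A reader might infer that any Visit 1 positive is counted. An isolated positive that is not confirmed does not meet 8.2.2.1.
- A reader might put the effect at 2 points by comparing 16/50 with 15/50. That replaces the boy with a negative one. Taking him out of both counts gives about 1.4 points.
- Prior blood-component exposure keeps the case possible but does not show it to be common. The 2011 protocol set no limit, and Amendment 7 added the 5 ED cap to keep the population homogeneous. Nothing in the documents contradicts the sponsor's view of the likelihood.
- Reaching 12 cases leads to committee review, which looks at how many exposures preceded each inhibitor. A case with none should be noticed, but only after enrolment has stopped.

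**Conclusion.** The point holds as a minor gap in the counting rule. A boy with no known history, a positive pre-dose Visit 1 sample and a positive confirmatory test is counted in the primary rate and towards the hold, although his inhibitor preceded the product. One such boy costs about 1.4 points on the primary estimate (with 15 incident cases assumed). It raises the chance of a hold from 4.4% to 7.4% at a 30% rate, or from 12.5% to 18.3% at 35%.

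The expected number of such boys is small and unknown, and the error makes the product look worse, not better. A reader might infer that the primary result is materially biased or made to look safer than it is. The documents support neither. The case for acting is that the stated rule gives a wrong attribution in a safety endpoint and that the correction uses data already collected.

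**What to change.** In 18.2.2, 18.2.4 and the hold rule (12.5.2 and 18.3), define an incident inhibitor as two consecutive central results of at least 0.6 BU/mL in samples taken after the first dose, in a patient who did not have a pre-dose Visit 1 positive confirmed at the next test. Then state that:

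- only patients whose pre-dose positive is followed by a consecutive positive confirmatory test leave the primary numerator and denominator and the hold count, and they are listed separately;
- patients with a missing or unevaluable baseline sample, and those whose baseline positive was not confirmed, stay in. Requiring a documented negative baseline would drop true on-treatment cases and lower a safety rate;
- a sensitivity analysis counts all confirmed cases regardless of baseline.

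The cost is a short definition in three places, one listing and one sensitivity analysis. The pre-dose sample is already required, and eligibility and dosing are not touched. The downside is that the denominator may fall slightly below 50 and the primary rate becomes slightly less conservative, which the sensitivity analysis makes visible.
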